8.3.2 Overall Survival

Overall survival (OS, reported in weeks) is defined as the interval between the date of randomization and date of death from any cause. Patients who are still alive or who are lost to follow-up will be censored at the date of last contact. As mentioned in [Section 3.1](#), OS will be analyzed during the entire study period in a similar fashion to PFS.

8.3.3 Time to Response

The time to response, based on the independent radiologic review, is defined as the interval between the date of randomization and the earliest date of first documented confirmed CR or earliest date of first documented confirmed PR if the patient does not have confirmed CR. Patients who do not have a confirmed PR or CR will be censored at the date of the last assessment during the double-blind treatment analysis period. Time to response will be summarized and displayed using KM methods in a manner similar to the primary analysis of PFS.

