2.3 Determination of Sample Size

The sample size selection of approximate 120 patients (n=80 DCC-2618, n=40 placebo) was based on considerations for powering of the primary endpoint, key secondary endpoint, detection of rare safety events and overall exposure to DCC-2618, and assuming 15% patient dropout. Patients will be randomized in a 2:1 ratio of DCC-2618 versus placebo.

This sample size [105 patients (n=70 DCC-2618, n=35 placebo) with 90 events (55 DCC-2618, 35 placebo) at the final analysis] will have at least 90% power to detect a difference in PFS between DCC-2618 and placebo assuming a median PFS of 4.5 months for DCC-2618 and 1 month for placebo. Moreover, this assumes 9 months of uniform recruitment and 6 additional months of follow-up (total patient follow-up of 15 months).

Furthermore, 105 patients (n=70 DCC-2618, n=35 placebo) will have approximately 80% power to detect a 0.2 difference in ORR assuming that the ORR for DCC-2618 = 0.22 and the ORR for placebo = 0.02.

In addition, a minimum sample size of 80 DCC-2618 patients allows adequate power to detect the incidence of rare safety events. A sample of 80 patients yields 95% probability that the study will reveal at least one occurrence of all safety events that occur in patients at a rate of 4.0% or greater. This in combination with the exposure to DCC-2618 from other studies conducted in this clinical program will meet the recommendations for overall exposure recommended by FDA.

Where required, safety personnel at the Sponsor or designee may be unblinded to a patient's study drug assignment to meet reporting requirements to regulatory agencies. In addition, the Investigator, patient, Sponsor, and study team will be unblinded at the time the patient has disease progression by modified RECIST based on independent radiology review.

At no point in time before official full study unblinding will any efficacy and safety analyses be conducted by the Sponsor or Sponsor representatives, unless there is explicit permission to do so, for instance high level efficacy assessment for the purposes of an Independent Data Monitoring Committee (IDMC) review to determine the adequacy of the risk/benefit profile of the drug as it pertains to the conduct of the clinical trial.

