3.1 Statistical Analysis Periods

Based on the study design, two main analysis periods will be defined as follows:

- Double-blind treatment analysis period
 - from the randomization date to the last follow-up date
 - if a patient did not have disease progression based on independent radiologic review or
 - if a placebo patient did not cross over to DCC-2618 treatment or
 - if a patient was initially treated with DCC-2618 and did not continue to receive DCC-2618 at 150mg QD or escalate to 150mg BID after disease progression based on independent radiologic review from the randomization date to the first disease progression date if a patient was initially treated with DCC-2618 and continued to receive DCC-2618 at 150mg QD after disease progression based on independent radiologic review
 - from the randomization date to the day immediately before the first dose of DCC-2618 150mg BID if a patient escalated to DCC-2618 150mg BID after disease progression based on independent radiologic review
 - from the randomization date to the day immediately before the first dose of DCC-2618 150mg QD if a patient crossed over from placebo to receive DCC-2618 at 150mg QD after disease progression based on independent radiologic review
- Open-label analysis period
 - from the day immediately after the first disease progression based on independent radiologic review to the last follow-up date if a patient was initially treated with DCC-2618 and continued to receive DCC-2618 150mg QD after disease progression based on independent radiologic review
 - from the first dose date of DCC-2618 150mg BID to the last follow-up date if a patient was initially treated with DCC-2618 and escalated to DCC-2618 150mg BID after disease progression
 - from the first dose date of DCC-2618 150mg QD to the last follow-up date if a patient crossed over from placebo to receive DCC-2618 150mg QD after disease progression based on independent radiologic review

The primary efficacy endpoint, progression-free survival, will be defined and analyzed only during the double-blind treatment analysis period.

Overall survival will be defined and analyzed throughout patients' entire on study period. The data cut-off for the primary analysis will occur when 90 PFS events have occurred. It is expected that the primary analysis will occur approximately 6 months after the last patient is enrolled into the trial.

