3.6 General Analysis Conventions

Continuous variables will be summarized using descriptive statistics (number of patients, mean, median, standard deviation, minimum, and maximum). Categorical variables will be summarized using frequencies and proportions. Time-to-event data will be summarized via Kaplan-Meier (KM) methodology using the 25th, 50th (median), and 75th percentiles with associated 2-sided 95% confidence intervals.

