treatment) after a patient discontinued treatment or withdrew for reasons other than progressed disease. For patients who have first disease progression documented between scheduled assessments, progression date is defined as the date of new lesion (if progression is due to new lesions) or defined as the earliest of the scan dates of the components that triggered the progression per independent radiologic review (if progression is due to increase in sum of measured lesions).

Analysis for PFS will be stratified by the randomization stratification factors [prior lines of therapy (3 versus ≥ 4) and ECOG (0 versus 1 or 2)]. The p-value will be from a 2-sided stratified Log-rank test at 0.05 significant level for evaluation of treatment difference. Point estimate of hazard ratio will be obtained from a Cox regression model with treatment and the randomization stratification factors as fixed factors and its 95% CI will be obtained using Wald method. PFS time will be summarized via KM methodology using the 25th, 50th (median), and 75th percentiles and pre-specified timepoints, each with associated 2-sided 95% confidence intervals.

Analyses will be performed using the ITT population as the primary efficacy analysis and PP population as supportive.

Sensitivity analyses maybe performed if deemed necessary.

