8.2 Key Secondary Endpoint

ORR is defined as the proportion of patients with a confirmed complete response (CR) or partial response (PR) based on the independent radiologic review and during the initial assigned study treatment. This analysis will be performed in the ITT population as the main analysis and the PP population as supportive analysis. To be assigned a status of a CR or PR, changes in tumor measurements must be confirmed by repeat assessments that must be performed at least 4 weeks (allowing a minus 3 day window) after the criteria for response are first met. This analysis will include assessments prior to an event or censoring under the primary PFS analysis. Patients with unknown or missing response will be categorized as non-responders and will be included in the denominator when calculating the proportion. An unstratified two-sided Fisher's Exact test at a 0.05 significance level will be used to investigate statistical differences between treatment groups.

A 95% Newcombe score confidence interval will be constructed for the treatment rate difference in ORR ([Newcombe, 1998](#))

A sensitivity analysis will be performed for ORR without requiring confirmation of CR and PR.

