8.3.7 Duration of Response

Duration of response is defined as the time interval from the first assessment of confirmed CR or PR until the first disease progression or death. In the case that the PFS is censored, duration of response will be censored at the last evaluable progression-free radiologic assessment in an analogous manner.

Duration of response based on the independent radiologic review will be analyzed with Kaplan-Meier method using the 25th, 50th (median), and 75th percentiles and survival probability at pre-specified timepoints, each with associated 2-sided 95% confidence intervals. Duration of response based on the Investigator assessment will be analyzed in a similar fashion as well.

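### Time to response is estimated by Kaplan-Meier with progressed and dead non-responders censored, so a 25th percentile can be printed although fewer than 25% of patients responded

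*SAP*

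**What the plan says.** SAP 8.3.3 measures time to response from randomization to first confirmed CR or PR by independent review. Its last two sentences set the censoring and the method: "Patients who do not have a confirmed PR or CR will be censored at the date of the last assessment during the double-blind" phase, and "Time to response will be summarized and displayed using KM methods in a manner similar to the primary analysis of PFS". There is no separate rule for progression or death. SAP 4.1 makes ITT the primary set for all efficacy analyses, so non-responders are in the estimate.

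The PFS summary being copied is in SAP 8.1: "PFS time will be summarized via KM methodology using the 25th, 50th (median), and 75th percentiles and pre-specified timepoints". The general convention in SAP 3.6 agrees: "Time-to-event data will be summarized via Kaplan-Meier (KM) methodology using the 25th, 50th (median), and 75th percentiles".

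SAP 8.3.3 does not itself say whether a response after progression would count. Two neighbouring sections bear on this. SAP 8.2 says for ORR: "This analysis will include assessments prior to an event or censoring under the primary PFS analysis". SAP 8.3.7 runs duration of response "from the first assessment of confirmed CR or PR until the first disease progression or death", which presupposes that response comes first. Under SAP 3.1 the double-blind period extends to last follow-up for some patients, for example "if a placebo patient did not cross over to DCC-2618 treatment".

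Protocol 9.8.5.2.1 also censors non-responders, but at the last adequate assessment and with the clock starting at first dose. Protocol 9.8.5.3.3 calls for KM and gives no censoring rule.

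**The concern.** KM treats a censored patient as someone who could still have the event at the same rate as those who remain. That is reasonable for a patient who is progression-free at data cut-off. It is not reasonable for a patient who has died, or for one who has progressed if response must precede progression. Those patients can no longer respond, yet KM redistributes their weight to the patients still at risk. Each later response then counts for more than one patient's share of the arm.

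A reader takes the 25th percentile as the time by which a quarter of the arm had responded. It can be printed beside an ORR below 25% in the same report. At stake is the meaning of a listed secondary summary, not a test.

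**Working it through.** **Inputs.** From SAP 2.3: ORR 22% on DCC-2618 and 2% on placebo; median PFS 4.5 and 1 month; 80 and 40 randomized; 70 and 35 in the power calculation; 9 months of uniform accrual plus 6 months of follow-up. From Protocol Table 1, footnote 21: scans each cycle to Cycle 4, then every other cycle, taken here as weeks 4, 8, 12, 20 and 28. The timing of responses is in neither document, so it is varied.

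**1. Reproduce the plan's event count.** With exponential PFS and λ = ln 2/median, expected events = n × [1 − (e^(−6λ) − e^(−15λ))/(9λ)].
- DCC-2618: λ = 0.1540 per month; 70 × 0.7853 = 54.97
- Placebo: λ = 0.6931 per month; 35 × 0.9975 = 34.91

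The total is 89.9, against the SAP's figures "with 90 events (55 DCC-2618, 35 placebo) at the final analysis". The progression model therefore matches the plan.

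**2. How much censoring is of the problem kind.** On DCC-2618 there are 70 × 0.22 = 15.4 responders and 54.6 non-responders. Even if every responder also has a PFS event, 55 − 15.4 = 39.6 of the 54.6 non-responders (73%) leave by progression or death.

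**3. Worked case.** Take 80 patients with 18 responders (22.5%): 5, 5, 4 and 4 at weeks 4, 8, 12 and 20. The 62 non-responders progress exponentially (median 4.5 months × 4.348 = 19.57 weeks, λ = 0.0354 per week). Each is censored at the scan that detects progression, so the risk set at a scan is the responders still to come plus 62 × e^(−λ × week of previous scan).

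| Week | At risk | Responses | 1−KM | Crude rate |
|---|---|---|---|---|
| 4 | 80.0 | 5 | 6.2% | 6.2% |
| 8 | 66.8 | 5 | 13.3% | 12.5% |
| 12 | 54.7 | 4 | 19.6% | 17.5% |
| 20 | 44.5 | 4 | 26.8% | 22.5% |

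1−KM = 1 − (1 − 5/80)(1 − 5/66.8)(1 − 4/54.7)(1 − 4/44.5) = 0.268. A 25th percentile prints at week 20, although 22.5% responded. With all 18 responses at week 4, 1−KM is 22.5% and nothing is distorted.

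**4. How often.** Simulation of the DCC-2618 arm: n = 80, 20,000 trials per case, the plan's accrual and follow-up, no other dropout. At each scan a response is drawn among patients still progression-free, with per-scan probabilities calibrated to the true ORR. The table gives the chance that 1−KM reaches 25% while the observed ORR is below 25%. Where a range is shown, the per-scan probability is constant or proportional to the scan interval.

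| Response timing (assumed) | ORR 22% | ORR 15% | ORR 10% |
|---|---|---|---|
| All at week 4 | 0% | 0% | 0% |
| Front-loaded 6:3:1 over weeks 4, 8, 12 | 8-9% | 1% | 0% |
| Spread to week 12 | 21-22% | 4% | 0.1% |
| Spread to week 28 | 42-52% | 14-23% | 1-2% |

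Equal numbers of responders at each scan gives slightly more: 26% (to week 12) and 55% (to week 28) at ORR 22%, and 25% (to week 28) at ORR 15%. The expected 1−KM plateau at ORR 22% runs down the rows as 0.220, 0.236, 0.253 and 0.287-0.307. The 15% column is suggested by Protocol 1.3.2.3: 5 PR among 33 patients at 100 mg daily or more, 5/33 = 15%.

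On placebo (ORR 2%, median PFS 1 month, n = 40) the chance is at most about 2%.

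**5. Same data, Aalen-Johansen.** With progression or death as the competing event, the contradiction occurs in at most 0.1% of trials in every DCC-2618 case.

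**The case against.** **Timing is assumed.** The documents say nothing about when responses occur, and at ORR 22% that choice alone moves the result from 0% to about 50%. The top figures need responses to continue undiminished to week 28. Requiring the next scheduled scan to be progression-free and before cut-off, as confirmation would, lowers the week-28 range to 39-48%. This stands: the percentages are illustrations, and only the mechanism is certain.

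**The 15% figure may be generous.** The Phase 1 responses are by local review, are not stated to be confirmed, and come from patients with one to seven prior therapies (Protocol 1.3.2). All doses together give 5/37 = 13.5%, where the chance is 0.4% front-loaded, 2% to week 12 and 8-17% to week 28. This also stands.

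**Competing-event status is inferred.** SAP 8.3.3 does not exclude responses after progression. A reader might infer that it does; the text supports this only by analogy with SAP 8.2 and 8.3.7. The inference is reasonable, and for death it needs no support.

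**It is a consistent convention.** The protocol already specifies KM, and SAP 8.3.1 names death as a competing risk for TTP and censors it there too. That explains the choice, but does not make the percentile mean what a reader will take it to mean.

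**The reader has the ORR.** SAP 8.2 reports the crude rate with all patients in the denominator, so a misreading can be corrected. This limits the harm and supports a minor grade.

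**Conclusion.** Wrong as written, and minor. Followed exactly, SAP 8.3.3 yields a curve that, if response counts only before progression, is never below the cumulative incidence of response. It lies above it whenever responses follow other patients' progression or death. A 25th percentile can then be printed when fewer than a quarter of patients responded.

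At the planned ORR and median PFS the chance in the DCC-2618 arm runs from 0% to about 40-50%, depending on response timing that the documents do not give. It is lower at ORR 15% (0% to about 23%) and at most about 2% at ORR 10%. These figures rest on exponential PFS, the scheduled scan weeks and no other dropout.

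A reader might go further and infer that the report will contain this contradiction, or that the ORR comparison is biased. The documents support neither. The first depends on unknown timing and vanishes if responses come at the first scan. For the second, ORR is a crude proportion tested by Fisher's exact test. Time to response is outside the hierarchy in SAP 8.5, so PFS, ORR and type I error are untouched. Censoring patients who are still progression-free at cut-off is also correct and should stay.

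**What to change.** Replace the last two sentences of SAP 8.3.3 with:

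> Only assessments admitted for ORR in Section 8.2 count. The cumulative incidence of confirmed response will be estimated by the Aalen-Johansen method, with a PFS event as defined in Section 8.1 (progression by independent radiologic review or death) before confirmed response as the competing event. Patients with neither a confirmed response nor a PFS event will be censored at their PFS censoring date under Section 8.1. Cumulative incidence at the pre-specified timepoints with 95% confidence intervals will replace the KM percentiles; the median and range of time to response will be given among confirmed responders.

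The link to Sections 8.1 and 8.2 matters. SAP 8.2 stops at PFS censoring as well as at a PFS event, and SAP 8.1 censors at resection, at other anticancer treatment and before two or more missed scans. If non-responders were instead censored at the last double-blind assessment, which can run to last follow-up, a response after new anticancer therapy could count here although ORR excludes it. A progression after two missed scans could likewise be treated as competing although the primary PFS analysis censors it.

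SAP 8.1 refers to the timepoints without listing them, so list them here. The cost is SAP wording and a standard procedure; no new data are needed.

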8.3.4 PFS Based on Investigator Assessment

As a sensitivity analysis to the primary efficacy analysis, PFS (reported in weeks) is defined as the interval between the date of randomization and the earliest documented evidence of disease progression based on Investigator assessment or death on initial study treatment due

to any cause. In the situations mentioned in [Section 8.1](#), PFS based on investigator assessment will be defined or censored in a manner analogous to which is used for PFS based on independent radiologic review.

PFS based on investigator assessment will be analyzed in similar fashion to PFS based on independent radiologic review.

8.3.5 Quality of Life

Quality of life (QOL) will be based on European Organisation for Research and Treatment of Cancer Quality of Life Questionnaire for Cancer 30-item (EORTC-QLQ-C30) and the EuroQol 5-Dimension 5-Level (EQ-5D-5L) questionnaires.

The EORTC-QLQ-C30 will be summarized by scale. In all scales, a high scale score represents a higher response level. The scoring for this questionnaire will be done in 2 steps.

1. Calculate the average of the items that contribute to the scale. This will be used as the raw score for the scale, and
2. Apply a linear transformation to standardize the raw score, so that scores range from 0 to 100.

Changes from baseline to Day 1 of Cycle 2 in EORTC-QLQ-C30 Role function and Physical function will be compared between the two treatment arms using analysis of covariance (ANCOVA) model with the stratification factors as factors. If Day 1 of Cycle 2 value is missing, then the change from baseline to the end of initial study treatment will be used in the analysis.

The EQ-5D-5L is a standardized measure of health status comprised of a descriptive system including five health-related QOL states (ie, mobility, self-care, usual activities, pain/discomfort, and anxiety/depression) and a visual analogue scale (VAS) of overall health. Each dimension is rated on a 5-point response scale indicating severity of problems, where 1 is “no problems”, 2 “slight problems”, 3 “moderate problems”, 4 “severe problems”, and 5 is “extreme problems”. The five questions are scored and together contribute to the EQ-5D-5L index (utility) score between 0 and 1 (1 being perfect health), which will be calculated using the developers’ algorithm based on country-specific reference score sets (Van Hout et al., 2012). Score sets are available for Denmark, France, Germany, Japan, Netherlands, Spain, UK, US and Zimbabwe. For countries in which no score set exists (Canada, Hungary, Israel, Romania, and Sweden) the closest neighboring country will be used as a proxy (EuroQol Group, 2015), eg, UK value set for Australia, France value set for Belgium, USA value set for Canada and Singapore, and Germany value set for Poland. If scale is missing for one of the dimensions, the index (utility) score will have a missing value.

EQ-5D-5L will be summarized overall by number and percentage for each level of each dimension. For pain/discomfort and usual activities, the Cochran–Mantel–Haenszel test will be used to test the change in response scale at Day 1 of Cycle 2 from baseline between DCC-2618 and placebo. For EQ-5D-5L index (utility) score, an ANCOVA model with the stratification factors as factors will be used to compare the change at Day 1 of Cycle 2 from baseline between the two treatment arms.

The EuroQol visual analogue scale (EQ-VAS) is a measure of overall self-rated health status, used and analyzed separately from the index score. The EQ-VAS recorded the subject’s self-rated health on a 20 cm vertical VAS with endpoints labelled “the best health you can imagine” and “the worst health you can imagine.” The EQ-VAS score ranges from 0 to 100,

with higher scores indicative of better overall health. EQ-VAS will be summarized using continuous descriptive statistics. Change in EQ-VAS score at Day 1 of Cycle 2 from baseline between the two treatment arms will be tested with a t-test.

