8.5 Multiple Comparisons/Multiplicity

To control familywise type-I error, the hypothesis tests for treatment difference between DCC-2618 and placebo will be performed at two-sided 0.05 level of significance sequentially in the following order:

1. The primary endpoint PFS based on independent radiologic review
2. The key secondary endpoint ORR based on independent radiologic review
3. OS
4. QOL as determined by changes from baseline to Day 1 of Cycle 2 in EORTC-QLQ-C30 Role function and Physical function (each at 0.025 level of significance)

If any hypothesis test is not significant at $\alpha=0.05$ level, the subsequently listed analyses will be viewed as descriptive.

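### The quality-of-life change analyses omit the baseline score as a covariate, and EQ-VAS gets an unadjusted t-test, which gives away precision and leaves part of any baseline imbalance in the estimate

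*SAP*

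**What the plan says.** SAP 8.3.5 (Quality of Life) takes the change to Cycle 2 Day 1 in QLQ-C30 Role and Physical function and states that these changes "will be compared between the two treatment arms using analysis of covariance (ANCOVA) model with the stratification factors as factors". The two factors are prior lines of therapy (3 versus ≥ 4) and ECOG (0 versus 1 or 2).

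The same section gives the EQ-5D-5L utility index the same treatment: "an ANCOVA model with the stratification factors as factors will be used to compare the change at Day 1 of Cycle 2". For EQ-VAS it says: "Change in EQ-VAS score at Day 1 of Cycle 2 from baseline between the two treatment arms will be tested with a t-test".

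SAP 8.5 places Role and Physical function fourth in a fixed sequence, after PFS, ORR and OS, with "each at 0.025 level of significance". The EQ-5D-5L index and EQ-VAS are not in that sequence.

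Nothing elsewhere supplies the missing covariate. SAP 3.3 defines what a baseline value is and SAP 3.6 gives summary conventions; neither makes baseline a model term. The QLQ-C30 model in protocol 9.8.5.3.5 (treatment, mutation and line status, ECOG) has no baseline QLQ-C30 score either. Both questionnaires are scheduled at Cycle 1 Day 1 in protocol Table 1.

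**The concern.** An analysis of change without the baseline score fixes the baseline coefficient at exactly 1. The best-fitting coefficient is usually smaller, because patients who start low on a bounded 0 to 100 scale tend to move up and those who start high tend to move down. Two consequences follow.

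- **Precision.** The residual variance is larger than it need be, so confidence intervals are wider and power is lower.
- **Conditional imbalance.** If one arm starts higher by chance, the change score over-corrects, and part of the imbalance stays in the treatment difference with the opposite sign. With about 40 placebo patients, such differences are not negligible.

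Two of the affected comparisons can carry a formal claim, and the sample-size sections (protocol 9.1, SAP 2.3) give no power for them. As written, one programmer could add baseline because the model is called an ANCOVA and another could leave it out, giving different p-values for the same confirmatory test.

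**Working it through.** **Inputs from the documents.** About 80 and 40 randomised (SAP 2.2.2); 70 and 35 after the planned 15% dropout (SAP 2.3); two-sided 0.025 per scale (SAP 8.5). The documents give no quality-of-life effect size, standard deviation, baseline correlation or power.

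**The plan's own figure.** 0.025 + 0.025 = 0.05, which matches the two-sided level of the sequence.

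**Assumptions.** ρ is the correlation between the baseline and Cycle 2 Day 1 scores, taken from 0.3 to 0.9. s1 and s2 are the standard deviations at the two visits.

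**Variance, general case.**
- Change score: s1² + s2² − 2ρ·s1·s2
- Baseline-adjusted: s2²(1 − ρ²)
- Difference: (s1 − ρ·s2)², which is never negative

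Apart from one degree of freedom, adjustment therefore cannot lose.

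**Equal standard deviations (s1 = s2 = s).** The ratio of adjusted to change-score variance is s²(1 − ρ²) / [2s²(1 − ρ)] = (1 + ρ)/2. The equivalent sample-size penalty for omitting baseline is 2/(1 + ρ) − 1, and the interval is wider by 1/√[(1 + ρ)/2] − 1. The last column gives the power of the adjusted test when the change-score test has 80% at 0.025.

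| ρ | Variance ratio | Extra patients needed | Interval wider by | Adjusted power |
|---|---|---|---|---|
| 0.3 | 0.65 | 54% | 24.0% | 94.3% |
| 0.5 | 0.75 | 33% | 15.5% | 90.6% |
| 0.7 | 0.85 | 18% | 8.5% | 86.5% |
| 0.9 | 0.95 | 5% | 2.6% | 82.2% |

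**Unequal standard deviations.** With s1 = 1 and s2 = 1.3:
- ρ = 0.7: change variance 1 + 1.69 − 1.82 = 0.870; adjusted 1.69 × 0.51 = 0.862; penalty about 1%.
- ρ = 0.5: 1 + 1.69 − 1.30 = 1.390; adjusted 1.69 × 0.75 = 1.268; penalty about 10%.

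With s2 = 0.8 and ρ = 0.7: 1 + 0.64 − 1.12 = 0.520; adjusted 0.64 × 0.51 = 0.326; penalty about 59%.

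**Chance imbalance, in baseline standard deviations.** The standard deviation of the difference in baseline means is √(1/70 + 1/35) = 0.21, or √(1/80 + 1/40) = 0.19. The part that stays in the change-score estimate is −(1 − ρ) times the imbalance. A one-standard-deviation imbalance at 70/35 shifts the estimate by 0.5 × 0.21 ≈ 0.10 at ρ = 0.5 and 0.3 × 0.21 ≈ 0.06 at ρ = 0.7.

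**Simulation.** 4,000 trials at 70/35, equal standard deviations, both strata in each model but unrelated to the score, assumed effect 0.5 standard deviations, two-sided 0.025.

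| | ρ = 0.5, change only | ρ = 0.5, adjusted | ρ = 0.7, change only | ρ = 0.7, adjusted |
|---|---|---|---|---|
| Type I error | 0.022 | 0.022 | 0.025 | 0.025 |
| Power | 55.4% | 68.8% | 79.5% | 85.4% |
| Slope of estimate on baseline imbalance | −0.49 | 0.01 | −0.31 | −0.01 |

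The slopes agree with −(1 − ρ) for the change score and zero after adjustment. Under no effect, all four mean estimates were within 0.003 of zero.

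**The case against.** The strongest reply is that the model sentence is incomplete rather than wrong. It lists class factors only and omits treatment too, which must be in the model; an ANCOVA normally has a continuous covariate, so baseline may have been intended. That is a fair reading for Role function, Physical function and the EQ-5D-5L index. The remedy is still to name the covariate. The argument does not reach EQ-VAS, where the t-test is explicit.

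Other points limit the size of the problem, and they stand:
- A change-score comparison in a randomised trial is valid. Type I error is kept and there is no bias on average; any bias is conditional on the imbalance observed.
- Change scores already remove much of an imbalance when ρ is high, and having ECOG in the randomisation and the model may absorb more.
- Cycles are 28 days (protocol 5.2), so a high ρ is plausible, and the gain is then small. It also shrinks if scores spread out at follow-up, as the s2 = 1.3 case shows.
- Step four is tested formally only if PFS, ORR and OS are all significant.
- The EQ-5D-5L index and EQ-VAS carry no alpha.

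None of these gives a reason to leave baseline out.

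**Conclusion.** The concern holds. Neither document names the baseline score in any of these models, and EQ-VAS is explicitly left unadjusted. The consequence is lost precision and avoidable sensitivity to chance imbalance, not a threat to validity. With equal standard deviations at the two visits, the loss is equivalent to 33% more patients at ρ = 0.5, 18% at 0.7 and 5% at 0.9. The documents fix neither ρ nor the ratio of standard deviations, so these figures show a range and are not a forecast. The direction does not depend on them: apart from one degree of freedom, the adjusted analysis is never less precise. The change is worth making mainly for Role and Physical function, because they can support a formal claim in a small 2:1 trial.

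**What to change.** In SAP 8.3.5, state the full model for Role function, Physical function and the EQ-5D-5L index: change to Cycle 2 Day 1 as the outcome, with treatment, the corresponding baseline score as a continuous covariate, and the two stratification factors. Replace the EQ-VAS t-test with the same model using baseline EQ-VAS. Make the change before full study unblinding.

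The cost is a line of SAP text and one degree of freedom per model. No new data are needed, and no patient is lost, because a change from baseline can only be computed for someone who has a baseline score. The 0.025 level per scale and the testing order are unaffected.
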